13.1.5. Sensory Function Assessment (Cold Test)

For the sensory function assessment, the subject's sensitivity to cold in the innervated dermatomes (L2, L3) (see [Appendix 7](#)) will be assessed at baseline, when the subject wakes up after surgery (general surgery subjects only), and at 2, 4, 12, 24, 36, 48, 60, and 72 hours after surgery, or until the subject's sensitivity to cold has returned in two consecutive evaluations.

The subject's skin will be wiped with ice or an alcohol pad. The subject will then be asked, "Does this feel cold - yes or no?"

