The number and percentage of subjects who are in each of the above categories will be summarized by treatment group. A chi-square test will be used to compare liposome bupivacaine to placebo for each of the categories.

Overall Benefit of Analgesia Score Questionnaire

The OBAS is calculated as follows:

1. Add all of the scores of questions one to six.
2. To this number, add four.
3. Subtract the score of question seven from this number.

Summary statistics will be provided by treatment group at each time point. A Wilcoxon Rank Sum test will be used to compare liposome bupivacaine to placebo.

Subject Satisfaction with Postsurgical Pain Control

Subjects will rate their satisfaction with postsurgical pain control as Extremely dissatisfied, Dissatisfied, Neither satisfied nor dissatisfied, Satisfied, or Extremely satisfied at 72 hours and on Day 30. The categories will be summarized by treatment group at each time point. A Wilcoxon Rank Sum test will be used to compare liposome bupivacaine to placebo.

Time to Sensitivity to Cold

Once a subject reports sensitivity to cold on two consecutive evaluations the subject will no longer be tested. The time to sensitivity to cold will be defined as the time of the first of two consecutive evaluations when the subject reports sensitivity to cold. Time to sensitivity to cold will be calculated from the end of surgery. If a subject never reports sensitivity to cold or never reports sensitivity to cold on two consecutive evaluations then the time will be

censored at 72 hours after the end of surgery or at the time of the last follow-up, whichever is earliest. Time of last follow-up will be defined as the later of (1) the last pain assessment, (2) the start time of the last rescue or concomitant medication, or (3) the start time of the last AE.

Time to sensitivity to cold will be analyzed by the Kaplan-Meier method. The n (%) of subjects with sensitivity to cold as well as the n (%) of censored observations will be presented for each treatment group. In addition, Kaplan-Meier estimates in terms of the median and its 95% CI, and the 25th and 75th percentiles will be presented for each treatment group. For Part 2, a log-rank test will be used to compare liposome bupivacaine to placebo.

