	SD	00.00	00.00	
	Median	0000	0000	
	Minimum, Maximum	000, 000	000, 000	
72 Hours	n	00	00	0.0000
	Mean	000.0	000.0	
	SD	00.00	00.00	
	Median	0000	0000	
	Minimum, Maximum	000, 000	000, 000	

CI = confidence interval; LB = liposome bupivacaine.

Note: The lower the score, the better the overall analgesic treatment.

[1] P-value is from a Wilcoxon Rank Sum test.

Reference: [Listing 16.5.3](#).

Pacira Pharmaceuticals, Inc.
402-C-323

Table 14.2.2.13-2 (Page x of Y)
Subject Satisfaction with Postsurgical Pain Control
Study Part 2
(Efficacy Analysis Set)

Time Point	Assessment	LB	Placebo	P-value [1]
		XXX mg (N=XX) n/N (%)	(N=XX) n/N (%)	
72 Hours	Extremely Dissatisfied (1)	00/00 (00.0)	00/00 (00.0)	
	Dissatisfied (2)	00/00 (00.0)	00/00 (00.0)	
	Neither Satisfied or Dissatisfied (3)	00/00 (00.0)	00/00 (00.0)	
	Satisfied (4)	00/00 (00.0)	00/00 (00.0)	
	Extremely Satisfied (5)	00/00 (00.0)	00/00 (00.0)	
Day 30	Extremely Dissatisfied (1)	00/00 (00.0)	00/00 (00.0)	
	Dissatisfied (2)	00/00 (00.0)	00/00 (00.0)	
	Neither Satisfied or Dissatisfied (3)	00/00 (00.0)	00/00 (00.0)	
	Satisfied (4)	00/00 (00.0)	00/00 (00.0)	
	Extremely Satisfied (5)	00/00 (00.0)	00/00 (00.0)	

LB = liposome bupivacaine. n/N = Number of subjects with a subject satisfaction score of 1, 2, 3, 4, or 5 / Number of subjects with a subject satisfaction score at the time point.

Note: Percentages are based on number of subjects with a score at the time point.

[1] P-value is from a Wilcoxon Rank Sum test.

Reference: [Listing 16.5.4](#).

Pacira Pharmaceuticals, Inc.
402-C-323

Table 14.2.2.14-2 (Page x of Y)
Time to Sensitivity to Cold
Study Part 2
(Efficacy Analysis Set)

	LB XXX mg (N=XX)	Placebo (N=XX)
Subjects with Sensitivity to Cold [n (%)]	00 (00.00)	00 (00.00)
Censored Observations [n (%)]	00 (00.00)	00 (00.00)
Quartiles (hours) [1]		
First Quartile (25% with Sensitivity to Cold)	000	000
Median (50% with Sensitivity to Cold)	000	000
Third Quartile (75% with Sensitivity to Cold)	000	000
Minimum, Maximum	00, 00*	00, 00*
95% CI of Median	(000, 000)	(000, 000)
P-value from Log-Rank Test	0.0000	0.0000

* indicates a censored observation.

CI = confidence interval; LB = liposome bupivacaine,

[1] Estimates from a Kaplan-Meier Analysis.

Reference: [Listing 16.5.5](#).

Pacira Pharmaceuticals, Inc.
402-C-323

Table 14.3.1.1-2 (Page x of Y)
Overview of Treatment-Emergent Adverse Events
Study Part 2
(Safety Analysis Set)

	Part 2			Part 1 and Part 2 Combined		

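### Return of cold sensation is seen only at spaced tests but analysed as an exact time, so the Kaplan-Meier medians and quartiles run late and the medians' 95% CIs cover well below 95%

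*SAP*

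**What the plan says.** Protocol 13.1.5 schedules the cold test at baseline, at wake-up for some subjects (Protocol 12.1 and 13.1.5 say general surgery, the Synopsis and 13.5 say general anesthesia), and then "at 2, 4, 12, 24, 36, 48, 60, and 72 hours after surgery". Testing stops once two consecutive tests are positive.

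The protocol's endpoint (12.2) is the proportion of subjects sensitive to cold at each time point. SAP 7.6.1 replaces it with a time-to-event variable and notes the change. SAP 7.6.2.3 says the time is "defined as the time of the first of two consecutive evaluations when the subject reports sensitivity to cold", and that "Time to sensitivity to cold will be calculated from the end of surgery". Subjects without two consecutive positive tests are censored at 72 h or last follow-up, so a first positive at 72 h counts as censored.

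On method: "Time to sensitivity to cold will be analyzed by the Kaplan-Meier method". On output: "Kaplan-Meier estimates in terms of the median and its 95% CI, and the 25th and 75th percentiles will be presented for each treatment group". Part 2 adds a log-rank test. Table shells 14.2.2.14-1 and 14.2.2.14-2 print quartiles in hours and a row headed "95% CI of Median". Neither the section nor the shells name an interval-censored method or carry a caveat about test spacing.

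**The concern.** Each subject's return of sensation lies between the last negative test and the first confirmed positive one. The SAP records the right end of that interval as the event time. The error has one direction, so a larger sample does not remove it. Kaplan-Meier also treats the cluster of events around each test as precise information, so the CI for the median reflects sampling variation but not the width of the gap.

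These medians and quartiles are the only planned numerical estimate of how long the sensory block lasts, in a trial whose stated objective includes duration of effect. SAP section 2 allows planned analyses to go into study reports, submissions and manuscripts. A reader would take the printed median and CI at face value.

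**Working it through.** **Plan's own figures.** The plan states no expected median, hazard ratio or precision for this variable. Its only power figure is for the primary endpoint: 61 / (104 × √(2/90)) = 3.935, and Φ(3.935 − 1.96) = 97.6%. This agrees with the stated >97% but does not bear on this point.

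**Inputs from the documents.** Test times as above, giving gaps of 2, 2, 8 and then 12 h; 90 per arm in Part 2 and 25 in Part 1; two-sided 95% CIs (SAP 7.1); visit windows from ±15 min to ±4 h (Protocol Table 1). **Assumed:** the distribution of true return times, since the documents give none.

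**Lateness by hand.** If the reported median falls on the test that ends the gap, and the true median could lie anywhere in that gap, the average lateness is half the gap: 12/2 = 6 h, 8/2 = 4 h, 2/2 = 1 h.

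**Coverage by hand (90 subjects, log-normal, log-SD 0.5).**

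- True median 20 h. Recovered by 12 h: Φ(ln(12/20)/0.5) = 0.154, with 95% limits 0.154 ± 1.96 × √(0.154 × 0.846/90) = 0.08 to 0.23. Recovered by 24 h: Φ(ln(24/20)/0.5) = 0.642, limits 0.54 to 0.74. The 12 h limits lie wholly below 0.5 and the 24 h limits wholly above it. The CI for the median therefore sits around the 24 h test and misses 20 h.
- True median 25 h. Recovered by 24 h: Φ(ln(24/25)/0.5) = 0.468, limits 0.36 to 0.57, which include 0.5. Recovered by 36 h: Φ(ln(36/25)/0.5) = 0.767. The CI runs from about 24 to 36 h and contains 25 h.

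Coverage thus depends on where the true median falls in its gap, and on spread.

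**Simulation.** First positive test taken as the event, first positives at 72 h censored, Kaplan-Meier median with log-log 95% CI, visit windows applied, averaged over true medians 12.5 to 57.5 h:

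| Assumed return times | Median late, n=90 (h) | Coverage, n=90 | Coverage, n=25 |
|---|---|---|---|
| Weibull, shape 1 | 6.0 | 70% | 89% |
| Weibull, shape 1.5 | 6.0 | 59% | 82% |
| Weibull, shape 2 | 5.7 | 46% | 75% |
| Weibull, shape 3 | 5.9 | 29% | 58% |
| Log-normal, log-SD 0.5 | 6.2 | 35% | 65% |
| Log-normal, log-SD 0.8 | 6.2 | 57% | 78% |

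A tighter log-normal (log-SD 0.3, medians 13 to 49 h) gives about 20-27% at n=90 and about 40% at n=25. Single settings at n=90 run from near 0% to about 92%.

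- **Short medians.** For true medians of 0.5 to 4 h, coverage at n=90 is about 9%, but the miss is only 1 to 1.5 h. For 4.5 to 11.5 h, the median is 4.4 h late.
- **Quartiles** (n=90, log-normal, medians 13 to 49 h). The 25th percentile is 5.7-6.2 h late and the 75th is 4.4-5.5 h late.
- **Control.** With exact return times, coverage at n=90 was 92-96%, so the deficit comes from the test spacing.
- **Log-rank test.** Type I error on the visit-time data was 6.3% and 4.0% in 800 runs each. The Monte Carlo standard error is √(0.05 × 0.95/800) = 0.8%, so both agree with 5%.

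**The case against.** The strongest reply is that little depends on this. The variable is tertiary and outside the hierarchy. The definition says openly that the event is the time of an evaluation, and SAP 7.6.2.3 plans a plot of every Yes and No by subject and scheduled hour. All of that is true and limits the importance. It does not correct the printed medians or make a nominal 95% CI a 95% CI.

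Four stronger readings are tempting, and the documents do not support them.

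- **That the CIs mostly miss the true value.** This depends on spread, position and sample size. Among the six distributions tabulated, average coverage is below 50% in three at 90 per arm and in none at 25 per arm.
- **That the problem lies mainly in the liposome bupivacaine arm.** The documents give no return time for either arm. Spinal anesthesia is allowed, and either arm may receive femoral bupivacaine rescue for up to 12 h, so placebo returns need not be early. Where they are early, the placebo CI under-covers at least as badly, though by fewer hours.
- **That the CIs collapse to zero width.** This follows only if scheduled times are used. SAP 7.1.3 works from reported event times, and Listing 16.5.5 holds the date and time of each test. With the Table 1 windows, no simulated CI had zero width, and coverage barely moved.
- **That block duration is overstated on balance.** The clock starts at the end of surgery, while the block is given up to 2 h before surgery begins. The omitted time works the other way. The bias shown here is in time from end of surgery.

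The fix also has limits. A Weibull interval-censored fit gave 94-95% coverage when the truth was Weibull, but 86-92% coverage and 1.6-3.0 h bias when it was log-normal. Interpolating inside a gap rests on something the data cannot show. That argues for reporting the interval itself.

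**Conclusion.** The point holds as a reporting error in a tertiary variable. That the medians and quartiles run late follows from the schedule and the event definition alone. The size rests on the assumed distributions: about 6 h on average for a median in a 12 h gap (roughly 3 to 10 h by position) and about 1 to 1.5 h below 4 h. For true medians after 12 h, average CI coverage is about 20-70% at 90 per arm and about 40-90% at 25 per arm.

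If the liposome bupivacaine median lies after 12 h and the placebo median before 4 h, which is an assumption, comparing the two printed medians overstates the gap by about 6 − (1 to 1.5) = 4.5 to 5 h. No difference in medians is itself planned. A reader might infer that the between-arm test fails too. It does not: both arms share one schedule, and the simulated type I error is in line with 5%. No confirmatory conclusion changes.

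**What to change.** In SAP 7.6.2.3 and Tables 14.2.2.14-1 and 14.2.2.14-2:

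1. Enter each subject as an interval from the last negative test to the first confirmed positive test. Left-censor those positive at the first postsurgical test, and right-censor those never confirmed at their last negative test.
2. Estimate the median and quartiles with the Turnbull estimator and print each as the test interval it falls in, for example 24 to 36 h.
3. Move the lower CI limit for the median back to the previous test. Applied to the Kaplan-Meier CI in the simulations, this gave 99-100% coverage: conservative, with no distributional assumption.
4. Also report the protocol's proportion sensitive at each time point. State that subjects whose testing stopped after two positive tests count as sensitive from then on; otherwise the later denominators keep only those not yet recovered.
5. Keep the log-rank test.

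The cost is SAP wording and one programming step on data already in Listing 16.5.5. The downside is that durations will look wider and less precise, which is what the test schedule supports.

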
Methodology (Cont):
 
Part 1
 
During Part 1 of the study, approximately 100 subjects (25 per treatment arm) will be randomized to receive a single dose injection femoral nerve block with either one of three doses of liposome bupivacaine (67, 133, or 266 mg) or placebo in 20 mL under ultrasound guidance. Preservative-free normal saline will be added to the 67 mg and 133 mg doses of study drug to achieve a volume of 20 mL.
 
After all subjects have completed the 72-hour assessments in Part 1, an analysis will be conducted in order to select a single therapeutic dose from the three liposome bupivacaine dose levels tested. An unblinded dose selection committee will review at least the results from the following assessments conducted during Part 1: (1) the area under the curve (AUC) of the numeric rating scale (NRS) at rest (NRS-R) pain intensity scores through 72 hours; (2) total postsurgical opioid consumption; (3) the time to first opioid rescue; and (4) safety data. Based on a clinical evaluation of the data, the committee will determine the apparent efficacy and safety of each of the three liposome bupivacaine dose levels tested and will recommend a dose level for Part 2 of the study. Statistical significance will not be required in order to recommend a dose level for Part 2. The unblinded dose selection committee also will recommend whether the sample size for Part 2 should be increased.
 
Part 2
 
In Part 2 of the study, approximately 180 subjects (randomized 1:1, resulting in approximately 90 liposome bupivacaine subjects and 90 placebo subjects) will receive a single dose injection femoral nerve block with the selected dose level of liposome bupivacaine (i.e., 67, 133, or 266 mg) or placebo in 20 mL under ultrasound guidance.
 
Postsurgical Rescue Medication
 
Subjects should only receive rescue medication upon request for pain control, as needed.
 
The first rescue medication will be intravenous (IV) hydromorphone 0.5 mg, which will be administered once via bolus only. At this time, the PCA should be loaded with opioid (morphine or hydromorphone only).
 
The second rescue medication will be an on-demand PCA-administered opioid (morphine or hydromorphone). The PCA pump will be programmed to deliver either on-demand morphine or on-demand hydromorphone boluses at a dose and lockout interval in accordance with the site's standard practice. A continuous infusion (background or basal rate) of morphine or hydromorphone is not permitted. If the subject's pain is excessive or pain control is inadequate, then the bolus dose may be adjusted according to local hospital practices; however, adding a basal rate is prohibited. Once a subject is tolerating oral (PO) medication, PO immediate-release oxycodone may be administered (but not more than 10 mg every 4 hours).
 
If a subject's pain is inadequately controlled by opioids, a third rescue medication consisting of conventional bupivacaine HCl at a concentration of 0.125% (1.25 mg/mL) at a rate of 8 mL per hour for up to 12 hours may be administered via the previously placed femoral nerve catheter.
 
Subjects who do not achieve adequate pain relief with this regimen will be withdrawn from the study and followed for AEs only. No other analgesic agents, including non-steroidal anti-inflammatory agents (NSAIDs), are allowed during the 72-hour observation period or until the subject is withdrawn from the study, whichever is sooner.
		

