Appendix 6: Opioid-Related Adverse Events Questionnaire

The opioid-related adverse events questionnaire will be completed at 72 hours after surgery during Part 1 only. The subject will be asked the questions below.

Since your operation, have you had:

[figure not shown]
- Itching all over your body? Yes No
- Excessive tiredness? Yes No
- Difficulty breathing? Yes No
- Did you need a postsurgical bladder catheter? Yes No
- Vomiting? Yes No
- Need for medicine to prevent vomiting? Yes No
- Constipation? Yes No
- Confusion? Yes No
- Delirium? Yes No

If the subject answers "Yes" to any of these questions, the event should be recorded as an AE.

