7.6.1. Efficacy Variables

The primary efficacy variable is the AUC of the NRS-R pain intensity scores through 72 hours.

Secondary efficacy variables are:

- Total postsurgical opioid consumption (in mg) through 72 hours.
- Time to first opioid rescue.

Tertiary efficacy variables are (the order of these variables has been changed from the order in the protocol to reflect how they will be discussed in the CSR):

- The NRS-R and NRS-A pain intensity scores at each assessed time point.
- The AUC of the NRS-R pain intensity scores through 24, 36, 48, and 60 hours.

- The AUC of the NRS-A pain intensity scores through 24, 36, 48, 60, and 72 hours.
- The AUC of the NRS-R pain intensity scores from 24-48 and 48-72 hours.
- Proportion of subjects who are pain free (defined as an NRS pain intensity score of 0 or 1) at each assessed time point.
- Total postsurgical opioid consumption (in mg) through 24, 36, 48, and 60 hours.
- Proportion of subjects who receive the following rescue medication(s):
 - Subjects who receive no rescue medications (i.e., opioid or conventional bupivacaine HCl).
 - Subjects who only receive IV hydromorphone bolus.
 - Subjects who receive IV hydromorphone bolus and a second opioid medication.
 - Subjects who receive IV hydromorphone bolus, a second opioid medication, and conventional bupivacaine HCl.
- Overall benefit of analgesia score questionnaire at 24, 48, and 72 hours.
- Subject satisfaction with postsurgical pain control at 72 hours and Day 30.
- Time to sensitivity to cold (listed in the protocol as proportion of subjects at each time point with sensitivity to cold on one of the dermatomes).
- Incidence of predefined treatment-emergent ORAEs (diffuse pruritus, overt respiratory depression, urinary retention as measured by need for postsurgical bladder catheterization, constipation, sedation, confusion, delirium, vomiting, or need for antiemetic medication) at 72 hours (Part 1 only).

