7.6.2.3 Tertiary Efficacy Variables

For Part 1, no statistical tests will be performed on any of the tertiary efficacy variables. Only descriptive statistics will be shown for each treatment.

For Part 2, the following describes the statistical analyses to be performed.

NRS-R, NRS-A, and AUC of Pain Intensity Scores

For the tertiary efficacy variables NRS-R, NRS-A, and the AUCs of the NRS-R and NRS-A pain intensity scores, the same analyses as those for the primary efficacy variable will be performed, except that the baseline NRS-A score will be used as the covariate for all variables using the NRS-A.

Proportion of Subjects Who are Pain Free

Pain free is defined as an NRS-R pain intensity score of 0 or 1. The number and percentage of subjects who are pain free will be summarized by treatment group for each time point. A chi-square test will be used to compare liposome bupivacaine to placebo.

Total Postsurgical Opioid Consumption Through 24, 36, 48, and 60 Hours

For the tertiary efficacy variables total opioid consumption through each of the time periods, the same analysis as that for the secondary efficacy variable of total opioid consumption through 72 hours will be performed.

Subjects Who Receive Rescue Medication

The category of ‘Subjects who receive no rescue medication’ is defined as subjects who report not taking any medication on the four Rescue Medication eCRFs.

The category of ‘Subjects who only receive the IV hydromorphone bolus’ is defined as subjects who report taking IV hydromorphone (or other opioid medications) on the First Rescue Medication eCRF and report not taking a medication on either of the Second Rescue Medication eCRFs or on the Third Rescue Medication eCRF.

The category of ‘Subjects who receive the IV hydromorphone bolus and a second opioid medication’ is defined as subjects who report taking IV hydromorphone (or other opioid medication) on the First Rescue Medication eCRF and who report taking a medication on either of the Second Rescue Medication eCRFs and report not taking a medication on the Third Rescue Medication eCRF.

The category of ‘Subjects who receive the IV hydromorphone bolus, a second opioid medication, and conventional bupivacaine HCl’ is defined as subjects who report taking IV hydromorphone (or other opioid medication) on the First Rescue Medication eCRF, who report taking a medication on either or both of the Second Rescue Medication eCRFs, and bupivacaine HCl on the Third Rescue Medication eCRF.

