A plot of the responses to cold sensitivity will be produced for Part 1 and Part 2 separately. The x-axis will show the scheduled hours post-op. The y-axis will be the subject number. An 'X' will be plotted for responses of 'Yes' and an 'O' will be plotted for responses of 'No'.

Figures should be created by site and treatment, combining sites with few subjects, in order to show about 20 subjects per figure.

Incidence of Predefined Treatment-Emergent Opioid-Related AEs

The determination of whether a subject had a treatment-emergent ORAE will be based solely on responses on the Predefined Treatment-Emergent ORAEs eCRF. This was collected in Part 1 only. The number and percentage of subjects who have at least one ORAE will be summarized by treatment group. A chi-square test will be used to compare liposome bupivacaine to placebo.

The number and percentage of subjects who have each of the ORAEs will also be summarized by treatment group, although no statistical tests will be performed.

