Note: Percentages are based on number of subjects with a score at the time point.

Reference: [Listing 16.5.4](#).

Pacira Pharmaceuticals, Inc.
402-C-323

Table 14.2.2.14-1 (Page x of Y)
Time to Sensitivity to Cold
Study Part 1
(Efficacy Analysis Set)

	LB 67 mg (N=XX)	LB 133 mg (N=XX)	LB 266 mg (N=XX)	Placebo (N=XX)
Subjects with Sensitivity to Cold [n (%)]	00 (00.00)	00 (00.00)	00 (00.00)	00 (00.00)
Censored Observations [n (%)]	00 (00.00)	00 (00.00)	00 (00.00)	00 (00.00)
Quartiles (hours) [1]				
First Quartile (25% with Sensitivity to Cold)	000	000	000	000
Median (50% with Sensitivity to Cold)	000	000	000	000
Third Quartile (75% with Sensitivity to Cold)	000	000	000	000
Minimum, Maximum	00, 00*	00, 00*	00, 00*	00, 00*
95% CI of Median	(000, 000)	(000, 000)	(000, 000)	(000, 000)

* indicates a censored observation.

CI = confidence interval; LB = liposome bupivacaine,

[1] Estimates from a Kaplan-Meier Analysis.

Reference: [Listing 16.5.5](#).

Pacira Pharmaceuticals, Inc.
402-C-323

Table 14.2.2.15-1 (Page x of Y)
Incidence of Predefined Treatment-Emergent Opioid-Related Adverse Events
Study Part 1
(Efficacy Analysis Set)

	LB 67 mg (N=XX) n (%)	LB 133 mg (N=XX) n (%)	LB 266 mg (N=XX) n (%)	Placebo (N=XX) n (%)
Subjects with at Least One Event	00 (00.0)	00 (00.0)	00 (00.0)	00 (00.0)
Diffuse Pruritus	00 (00.0)	00 (00.0)	00 (00.0)	00 (00.0)
Overt Respiratory Depression	00 (00.0)	00 (00.0)	00 (00.0)	00 (00.0)
Urinary Retention [1]	00 (00.0)	00 (00.0)	00 (00.0)	00 (00.0)
Constipation	00 (00.0)	00 (00.0)	00 (00.0)	00 (00.0)
Sedation	00 (00.0)	00 (00.0)	00 (00.0)	00 (00.0)
Confusion	00 (00.0)	00 (00.0)	00 (00.0)	00 (00.0)
Delirium	00 (00.0)	00 (00.0)	00 (00.0)	00 (00.0)
Vomiting	00 (00.0)	00 (00.0)	00 (00.0)	00 (00.0)
Need for Antiemetic Medication	00 (00.0)	00 (00.0)	00 (00.0)	00 (00.0)

LB = liposome bupivacaine.

[1] Urinary retention was measured by need for postsurgical bladder catheterization.

Reference: [Listing 16.5.6](#).

Pacira Pharmaceuticals, Inc.
402-C-323

Table 14.2.3.1-1 (Page x of Y)
Bupivacaine Plasma Concentrations (ng/mL)
Study Part 1
(PK Analysis Set)

Time Point	Statistics	LB 67 mg (N=XX)	LB 133 mg (N=XX)	LB 266 mg (N=XX)
Baseline	n	00	00	00
	Mean	000.00	000.00	000.00
	SD	0.000	0.000	0.000
	%CV	000.00	000.00	000.00
	Median	0.00	0.00	0.00
	Minimum, Maximum	00.0, 00.0	00.0, 00.0	00.0, 00.0
15 Minutes	n	00	00	00
	Mean	000.00	000.00	000.00
	SD	0.000	0.000	0.000
	%CV	000.00	000.00	000.00
	Median	0.00	0.00	0.00

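### Part 1 opioid-event table: two of nine rows carry labels stronger than the question asked, subjects never asked count as event-free by default, and a test is planned that the SAP elsewhere rules out

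*SAP*

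**What the plan says.** Protocol Appendix 6 fixes the timing: "The opioid-related adverse events questionnaire will be completed at 72 hours after surgery during Part 1 only". The subject answers nine yes/no questions, one of which reads "Difficulty breathing? Yes No". Another asks about excessive tiredness.

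SAP 7.6.1 lists the resulting variable in clinical terms, including "overt respiratory depression, urinary retention as measured by need for postsurgical bladder catheterization, constipation, sedation". Table 14.2.2.15-1 and Listing 16.5.6 carry the same terms, so the breathing question appears as "Overt Respiratory Depression". SAP 7.6.2.3 closes off any other source: "The determination of whether a subject had a treatment-emergent ORAE will be based solely on responses on the Predefined Treatment-Emergent ORAEs eCRF".

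The table shell is a plain n (%) layout under N for the efficacy analysis set. SAP 6 defines that set by dosing and surgery only, with no requirement for a 72-hour assessment. SAP 7.1 makes the total number of subjects in the population the general denominator unless something else is specified, and nothing else is specified for this table.

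On testing, SAP 7.6.2.3 states that for Part 1 "no statistical tests will be performed on any of the tertiary efficacy variables". Later in the same section it assigns a chi-square test of liposome bupivacaine against placebo to this variable, immediately after noting that it was collected in Part 1 only.

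**The concern.** Three things do not fit together.

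- **Labels.** A reader of the study report would take a row headed respiratory depression or sedation as something a clinician assessed. The rule requires only the subject's own yes, recalled at 72 hours.
- **Denominator.** A subject who left before 72 hours has no questionnaire, yet stays in the efficacy set and falls by default into the no-event group. Withdrawal need not be unrelated to treatment: the protocol withdraws subjects whose pain is not controlled by the rescue regimen, and lack of efficacy is a listed reason for early termination in the disposition table.
- **Testing.** Two statements in one SAP section conflict on whether a p-value is produced.

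The table matters more than its tertiary rank suggests in one respect. SAP 7.8.1 keeps adverse events solicited by this questionnaire out of the treatment-emergent tables and puts them in listings only. Table 14.2.2.15-1 is therefore their only tabulated summary, and no other table would correct it.

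**Working it through.** The documents give no opioid-event rate, no withdrawal rate and no power figure for this variable, so there is no stated figure to reproduce. The check has three parts.

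**1. Questions against row labels** (Appendix 6 against Table 14.2.2.15-1). There are nine questions and nine rows, matching one to one.

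| Question topic | Row label | Comparison |
|---|---|---|
| Difficulty breathing | Overt respiratory depression | Stronger; no footnote |
| Excessive tiredness | Sedation | Stronger; no footnote |
| Bladder catheter needed | Urinary retention | Relabelled, but defined in SAP 7.6.1 and footnoted |
| Itching all over | Diffuse pruritus | Near-synonym |
| Medicine against vomiting | Need for antiemetic | Near-synonym |
| Vomiting, constipation, confusion, delirium | Same words | No change |

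So two of nine labels say materially more than the question. Relabelling changes no count and no percentage.

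**2. Denominator.** Inputs:

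- Part 1 plans 25 subjects per arm (protocol synopsis).
- The default denominator is the full set (SAP 7.1, SAP 6).
- The procedures at withdrawal before 72 hours (protocol 10.3 and 13.6) do not include this questionnaire.
- m, the number per arm not asked, is not in the documents. It is assumed to range from 0 to 5.

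With x subjects answering yes, the tabulated rate is x/25 and the rate among those asked is x/(25 − m). Hence tabulated rate = (rate among those asked) × (25 − m)/25, and the relative understatement is m/25.

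| m | Factor (25 − m)/25 | 60% among those asked is shown as | Relative understatement |
|---|---|---|---|
| 0 | 1.00 | 60.0% | 0% |
| 1 | 0.96 | 57.6% | 4% |
| 2 | 0.92 | 55.2% | 8% |
| 3 | 0.88 | 52.8% | 12% |
| 5 | 0.80 | 48.0% | 20% |

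Unequal loss: assume 1 of 25 not asked on active and 5 of 25 on placebo, with the same rate among those asked in both arms. The gap is rate × (0.96 − 0.80).

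- Rate 40%: 38.4% against 32.0%, a gap of 6.4 points.
- Rate 60%: 57.6% against 48.0%, a gap of 9.6 points.
- Rate 80%: 76.8% against 64.0%, a gap of 12.8 points.

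In this example placebo looks better. With the losses reversed, active would.

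How much the unasked could matter: with x = 10 and m = 5, the table shows 10/25 = 40%, the rate among those asked is 10/20 = 50%, and the full-set rate could lie anywhere from 10/25 = 40% to 15/25 = 60%. The default always reports the lower end of that range.

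Other tables in the same SAP avoid this. The pain-free and subject-satisfaction tables (14.2.2.9-1 and 14.2.2.13-1) show n/N with N the subjects who have a score, and the physician-satisfaction table (14.3.5-1) says so in a note.

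**3. Testing.** SAP 7.6.2.3 rules out tests on Part 1 tertiary variables, and protocol 15.6.3.3 says the same for Part 1 categorical measures. The chi-square sentence applies to a variable that exists only in Part 1. It does not say which of the three doses is compared with placebo, and the shell of Table 14.2.2.15-1 has no p-value row.

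**The case against.** The strongest case against the point is that it is small and partly conditional. Most of that stands.

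- A reader might infer that all nine answers are turned into diagnoses. They are not: four keep their own words, two are near-synonyms and the catheter item is disclosed.
- A reader might infer that the Part 1 rates are wrong. The documents do not show this. The number not asked is unknown, subjects are required to stay on site for at least 72 hours, and with nobody missed the error is zero. The SAP 7.1 rule is worded as a general default and the table is only a shell, so the denominator is inferred.
- The eCRF is not among the documents. Its wording is inferred from Appendix 6.
- It is tempting to say that nobody assesses respiratory depression or sedation, and to take these rows only from investigator-recorded adverse events. That does not work. Investigators record adverse events through Day 30, including for withdrawn subjects, and unsolicited ones are already tabulated under SAP 7.8.1. Appendix 6 also requires each yes to be recorded as an adverse event, so the proposed source either brings the questionnaire answers back in or repeats an existing table.
- The variable is tertiary and Part 1 only, is not among the tables listed for the dose selection committee in SAP 7.9, and plays no part in the Part 2 tests. Evidence on opioid use comes from the secondary endpoint of total consumption.

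None of this removes the two unsupported labels, the default that treats an unasked subject as event-free, or the contradiction on testing.

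**Conclusion.** The point holds in a limited form. Two of nine rows are labelled more strongly than the question supports. By the stated default, event rates may be understated by a relative 0% to 20% if 0 to 5 of 25 per arm are not asked, and unequal withdrawal would add a spurious difference between arms. That range is an assumption, and the result also rests on reading the SAP 7.1 default as applying to this table. The contradiction on testing needs no assumption.

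The documents do not support saying that the rates are wrong or that the questionnaire as a whole is reported as diagnoses. The consequence is confined to one descriptive Part 1 table. It is worth correcting because that table is the only tabulated summary of these solicited events and the correction is nearly free.

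**What to change.** 1. In SAP 7.6.1, Table 14.2.2.15-1 and Listing 16.5.6, label the rows with the Appendix 6 question wording. Alternatively keep the terms and footnote the question, as is already done for urinary retention.
2. In Table 14.2.2.15-1, report n/N with N the subjects who completed the 72-hour questionnaire, and add a row for the number not asked in each arm, so that a reader can see how far the unasked could move each rate.
3. In SAP 7.6.2.3, delete the chi-square sentence for this variable.

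The cost is SAP text, one table template and one listing template. No new data are needed, and no other analysis changes.
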